## **3** STUDY IMPLEMENTATION

## 3.1 STUDY DESIGN

This is a randomized, double blind, placebo-controlled, pilot study of clobetasol 0.05% topical oral rinse with an open label cross-over or extension period. Consenting subjects with clinically significant oral chronic GVHD will be randomized to clobetasol 0.05% or placebo oral rinse. The placebo will be flavored with quinine, to approximate the "bitter" taste of clobetasol.

Subjects will be evaluated at bi-weekly intervals while on the study intervention. OMRS score will serve as the primary outcome measure. At the first 2 week interim appointment patients will be unblinded and started on the clobetasol oral rinse open label. In the absence of progressive oral disease on the scheduled interim evaluations during the 4-week clobetasol treatment period, all patients will complete a total of 4 weeks of treatment with clobetasol. Therefore, patients who were originally assigned to clobetasol arm will receive additional 2 weeks of treatment, and patients assigned to placebo arm will undergo an additional 4 weeks of treatment with clobetasol after unblinding. Patients with progressive disease after 2 weeks of therapy with clobetasol will be considered non-responders, taken off-treatment and treated as appropriate in consultation with primary clinician. Within 90 days of the end of the 1 month of treatment, all patients with evidence of benefit (response or stable disease) will be given an option to continue treatment with clobetasol 0.05% with or without additional treatment as deemed clinically necessary for 1 month after the conclusion of the initial treatment period. Additional follow-up appointment will be scheduled for all patients 1 month after completion of treatment. The change in OMRS scores from baseline to 4 weeks of mouth rinse usage will be the primary outcome variable. For the placebo group, the OMRS score at the end of the blinded phase/beginning of clobetasol rinse use (day 14) will serve as the baseline for the primary outcome. Difference in OMRS score between the groups (placebo and clobetasol) at the end of the 14-day blinded phase will serve as a secondary outcome measure. The study schedule of events is outlined in Appendix G.

# 

#	Because of problems with your teeth, denture or mouth have you	Never (0)	Hardly ever (1)	Occasionally (2)	Often (3)	Very Often (4)
1	Had trouble pronouncing words					
2	Felt sense of taste has worsened					
3	Had painful aching in the mouth					

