## 3.3.1 **Pre-Treatment Evaluation**

Pre-treatment tests should be performed within 1 month prior to enrollment on the trial unless otherwise stated. Evaluation may be performed as part of enrollment onto NIH Protocol #04-C-0281 entitled: "Prospective Assessment of Clinical and Biological Factors Determining Outcomes in Patients with Chronic Graft-Versus-Host Disease." All attempts will be made to enroll patients on this study; however evaluation may be done as part of any ongoing NCI protocol. A 7-day washout period is required if patients are currently using another oral topical treatment for mouth lesions.

- 1. Optional History and Physical Examination
- 2. NIH global scoring and data collection, including prior and concurrent therapy, (Appendix H)
- 3. Chronic GVHD NIH organ staging
- 4. Assessment of oral GVHD using OMRS and oral cGVHD Clinical Scoring Instrument (Appendix A and Appendix B)
- 5. Numeric rating scales for (0 to 10) for oral pain, oral sensitivity, and oral dryness

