## **Appendix C**)

- 6. Oral Global Scale (Appendix D)
- 7. Painometer (POM) Assessment (Appendix E)
- 8. Oral Health Impact Profile- OHIP-14 (Appendix F)
- 9. Hematology: Complete blood counts, with differential and platelet count. Within 72 hours prior to initial evaluation.
- 10. Chemistries: Electrolytes (including sodium, potassium, chloride, CO2, calcium, phosphorus and magnesium), creatinine, BUN, glucose, SGOT, alkaline phosphatase, SGPT, bilirubin, PT/INR and PTT, serum cortisol level and TBNK panel. Within 72 hours prior to initial evaluation.
- 11. FSH, LH, TSH, T4, CMV by PCR, and HSV by PCR.
- 12. Urine or Serum Pregnancy test: For all females of childbearing potential. This test is to be performed within 7 days prior to enrollment on the trial.
- 13. Urine glucose Within 72 hours prior to initial evaluation.
- 14. Biopsy of buccal mucosa (4 mm punch) on patient's right side OR of buccal area with GVHD involvement for histopathological examination.
- 15. Research blood sample collection (18cc)
- 16. Five minute saliva sample, with and without paraffin stimulation
- 17. Short ACTH stimulation test, within 1 week prior to initial evaluation.
- 18. Clinical oral photo series
- 19. Adrenocorticotropic Hormone blood level within 1 week prior to initial evaluation.
- 20. Hemoglobin A1C level

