#### 3.3.3 End of Treatment Evaluation

The following tests and procedures should be performed at the end of scheduled open label treatment period (28 d.) or, if possible, at the time a patient comes off treatment regardless of the reason:

- 1. Optional History and Physical Examination
- 2. Assessment of oral GVHD using OMRS and oral cGVHD Clinical Scoring Instrument(Appendix A and Appendix B)
- 3. Numeric rating scales for (0 to 10) for oral pain, oral sensitivity, and oral dryness (Appendix C)
- 4. Oral Global Scale (Appendix D)
- 5. Painometer (POM) Assessment (Appendix E)
- 6. Oral Health Impact Profile- OHIP-14 (Appendix F)
- 7. Hematology: Complete blood counts, with differential and platelet count
- 8. Chemistries: Electrolytes (including sodium, potassium, chloride, CO2, calcium, phosphorus and magnesium), creatinine, BUN, glucose, SGOT, alkaline phosphatase, SGPT, bilirubin, PT/INR and PTT, HSV by PCR, cortisol level and TBNK panel.
- 9. Urine glucose
- 10. Research blood sample collection (18 cc)
- 11. Biopsy of buccal mucosa (4 mm punch) near baseline biopsy site
- 12. Five minute saliva sample, with and without paraffin stimulation
- 13. Clinical oral photo series
- 14. Short ACTH stimulation test
- 15. Adrenocorticotropic Hormone blood level
- 16. Hemoglobin A1C level

The goal of the day 28 biopsy is to assess microscopic and molecular changes associated with response (or lack thereof) to topical clobetasol for the purpose of potential cGVHD marker development. The primary response variable in this study is clinical grading of cGVHD.

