#### 5.1.2 Additional Analyses

Note: All samples will be sent for storage until analysis as detailed in Section 5.2 under appropriate storage conditions.

The oral tissue sections will be examined by a pathologist to assess oral cGVHD status. Half of the biopsy will be formalin-fixed and sent to pathology for H&E staining. One quarter will be flash frozen for analysis of gene expression, and one quarter will be frozen in OCT media, and both quarters will be stored until analysis. Immunohistochemical and PCR analysis will focus on characterization of cellular infiltrate, inflammatory cytokines, chemokines and protein mediators present at baseline and after clobetasol treatment.

Whole saliva samples will be examined for evidence of disease-related biomarkers associated with cGVHD and clobetasol treatment. Saliva will be collected in two 5-minute periods, one unstimulated and one stimulated with inert chewing (paraffin wax). The volume collected will be compared and used to indicate gland function.

Blood samples will be used to measure cortisol levels and in a subset of samples, to determine blood levels of clobetasol during treatment with the mouth rinse formulation. Heparinized plasma and cells will be stored for potential analysis of inflammatory markers and cellularity associated with cGVHD and clobetasol treatment.

One plasma sample (6 ml) will for LC-MS-MS analysis for clobetasol content.

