This study will aim to enroll a total of 34 evaluable patients randomized in a 1:1 fashion (17 per arm) to receive clobetasol rinse or placebo. The initial phase of the study will involve two weeks of either clobetasol rinse or placebo. At the end of the initial 2 weeks, patients receiving placebo will receive 28 days of clobetasol while those receiving clobetasol initially will receive an additional 14 days of clobetasol. Thus, each group will receive 28 days of clobetasol following either a 14 day placebo or immediately after randomization.

Patients will be randomized with a single stratification factor to try to ensure a balanced distribution among those getting placebo or not initially: being identified as having a high intensity of immunosuppression (2 or more agents/modalities  $\pm$  prednisone $\geq$ 0.5 mg/kg/day) vs. no or a lesser intensity of systemic immunosuppression according to the Intensity of Immunosuppression Scale . This scale was developed using expert opinion, and has been preliminarily demonstrated to have predictive validity as measure of the intensity of systemic immunosuppression. A low intensity regimen is defined as treatment with prednisone alone at a dose of less than 0.5 mg per kilogram per day. Moderately intense regimens include single agent prednisone at a dose greater than or equal to 0.5 mg per kilogram per day, and/or any other single agent or modality. Regimens comprised of two or more agents or modalities (+/- prednisone greater than or equal to 0.5 mg per kilogram per day), are categorized as highly intensive systemic immunosuppression. When scoring the intensity of systemic immunosuppression, the use of topical agents is not captured.

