The primary endpoint is the fraction of subjects who experience a 25% improvement in their OMRS compared to their own baseline. The fraction will be estimated with a two-tailed 95% confidence interval as the primary outcome. This will be done using all 34 patients together provided that the changes from baseline to day 28 for the two groups are sufficiently similar. A formal test will be performed assess their comparability. This will be determined conservatively, by obtaining the actual difference in the individual OMRS for each patient at baseline (day 0 for initial clobetasol and day 14 for those initially given placebo) vs. the value after day 28 of clobetasol and comparing those differences between the two randomized groups using a two-tailed Wilcoxon rank sum test. If the p-value for that comparison is >0.30, then the two groups will be considered sufficiently similar to allow pooling of the results and to report a combined

fraction of patients who have a 'response' to 28 days of clobetasol. In this case 34 patients will be sufficient to allow the proportion of patients with a response of 75% or more to have a two-sided 95% confidence interval of +/- 15% or less, which will be considered sufficiently precise. Fractions of responses <75% would have slightly wider confidence interval widths.

An important secondary endpoint is to compare the changes from day 0 in the OMRS until day 14 between those who only receive placebo by that point vs. those who received clobetasol. This evaluation will be done both with respect to the fraction with a response by 2 weeks, as well as comparing the actual changes in OMRS from day 0 to day 14.

By enrolling 17 patients per arm, a 0.10 alpha level one-tailed Fisher's exact test will have 80% power to detect a difference between a potential 75% of patients having a 25% or greater decrease in severity score on the clobetasol arm and about half that amount, 35%, on the placebo arm. A one-tailed test is sufficient for this secondary objective in this study since we will not expect clobetasol to be associated with a lower fraction of patients with benefit compared to placebo and because this is intended to be a pilot study to determine if a potential trend of magnitudes anticipated, but not necessarily a statistically significant gain, may be detected. Should very promising results be obtained, then a subsequent trial could be conducted to build upon and further confirm the benefit noted.

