A comparison of the actual levels of changes in the oral severity score between the arms will also be done using a Wilcoxon rank sum test as a secondary analysis. With 17 patients per arm, there is approximately 80% power to detect a difference between the arms in the changes from baseline to day 14 equal to one standard deviation of the change (effect size=1.0), using a two-tailed Wilcoxon rank sum test with a 0.05 significance level.

All patients will be placed on clobetasol for one month, whether following a two-week period with placebo or beginning at the time of randomization. In addition, comparisons between actual oral severity scores at the beginning of this period and one month later will be made using a paired t-test, or using a Wilcoxon signed rank test if the differences are not normally distributed (p<0.05 by Shapiro-Wilks test). These results will be evaluated separately according to the randomized treatment arm as well as overall if the changes in score according to the randomized assignments are similar (p>0.30 for Wilcoxon rank sum test comparing changes in scores between the two arms over the one month clobetasol period). Although this would also be considered a secondary evaluation, there would be 82% power to identify a 0.75 standard deviation change to be significant with a two-tailed 0.05 alpha level paired t-test if all 17 patients are available within each arm for this comparison.

Patients will undergo oral mucosa biopsies at the beginning of the study, and many are expected to have biopsies at the end of 28 days of treatment. Although required, these biopsies may not be obtained on all patients, and the number of patients with paired data will determine the differences in immunologic parameters from the biopsies that can be detected. For example, if there were 20 patients with paired biopsy data and 5 immunologic parameters of interest, each one would have 93% power to detect a change with an effect size of 1.0, with a very conservative two-tailed 0.01 significance level, to account for multiple comparisons. Fewer than 20 patients with paired biopsies would reduce the power accordingly, but since this is a secondary objective, the results of these tests will be presented in the context of an exploratory study.

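### In the placebo-first arm the paired biopsies span about 42 days, 14 of them on placebo, but response is measured over 28; Section 10.2 does not separate the pairs by arm

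*Combined protocol and SAP*

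**What the plan says.** **Biopsy timing.** Section 3.3.1 (item 14) lists the first biopsy as a pre-treatment test, with no difference by arm: "Biopsy of buccal mucosa (4 mm punch) on patient's right side OR of buccal area with GVHD involvement". Section 3.3.3 (item 11) lists the second at end of treatment: "Biopsy of buccal mucosa (4 mm punch) near baseline biopsy site". The interim list in Section 3.3.2 has no biopsy, and the Day 14 column of Appendix G is blank for it. A footnote to Appendix G gives placebo-first patients two such interim visits, the first at unblinding.

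**Treatment sequence.** After the two blinded weeks, Section 10.2 states that "patients receiving placebo will receive 28 days of clobetasol while those receiving clobetasol initially will receive an additional 14 days of clobetasol".

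**Response baseline.** For the placebo group, Section 3.1 says "the OMRS score at the end of the blinded phase/beginning of clobetasol rinse use (day 14) will serve as the baseline for the primary outcome". Section 10.2 repeats this and uses day 0 for the clobetasol-first arm.

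**Purpose of the tissue.** Objective 1.1.2.5 seeks tissue biomarkers of response or resistance to clobetasol. Section 3.3.3 gives the second biopsy the same purpose. Section 5.1.2 refers to mediators in tissue, including "protein mediators present at baseline and after clobetasol treatment".

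**Planned tissue analysis.** Section 10.2 introduces the pairs without reference to arm: "Patients will undergo oral mucosa biopsies at the beginning of the study, and many are expected to have biopsies at the end of 28 days". It then gives one worked example: 20 pairs, five parameters, each tested two-sided at 0.01, with 93% power at an effect size of 1.0. It says nothing about randomized arm for these pairs. In the preceding paragraph, the paired OMRS change is evaluated by arm, and overall only if a rank sum comparison of the arms gives p>0.30.

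**The concern.** The plan recognises that the arms reach clobetasol at different times, and for OMRS it moves the placebo-first baseline to day 14. Tissue cannot be re-baselined in that way because no biopsy is taken then. The tissue pair and the OMRS response therefore cover different intervals in one arm, and the tissue pairs cover different exposures in the two arms.

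Two consequences follow. First, a paired test across all pairs, read as change with clobetasol, also includes whatever happened in the tissue during two weeks of placebo. Second, a placebo-first patient who improves on placebo could show a tissue change with little OMRS response from day 14. That blurs the comparison of responders with non-responders which objective 1.1.2.5 needs.

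**Working it through.** **1. Reproduce the plan's figure.** Inputs from Section 10.2: n = 20 pairs, effect size 1.0, five parameters. The significance level is 0.05/5 = 0.01. Paired t-test power from the noncentral t distribution, with df = 19 and noncentrality 1.0 × √20 = 4.47, is 93.2%. The stated 93% is right for its inputs.

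**2. Count the days** (from day 0, using the sequence in Section 10.2).

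| | Clobetasol-first | Placebo-first |
|---|---|---|
| Tissue pair, nominal | 28 days | 14 + 28 = 42 days |
| Days on placebo within the pair | 0 | 14 (14/42 = 33%) |
| OMRS response interval | 28 days | 28 days (from day 14) |

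Section 3.3.4 confirms the end dates: follow-up 28 days after treatment falls at day 56 (28 + 28) or day 70 (42 + 28), by randomization group.

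**3. Does the example imply combining arms?** Section 10.2 plans 17 evaluable patients per arm. Twenty pairs must therefore include at least 20 − 17 = 3 from each arm.

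**4. How placebo-period change enters a pooled mean.** Let d be the mean tissue change during the placebo weeks, in SDs of the paired change, and assume it adds to the change on clobetasol. With m placebo-first pairs out of 20, the pooled mean is the clobetasol-period change plus (m/20) × d. For m = 10 this adds 0.5d; for m = 3 to 17 it adds 0.15d to 0.85d.

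**5. Illustration of the effect on the test.** The documents give no value for d, so these are assumptions: 10 + 10 pairs, SD 1, two-sided 0.01, 200,000 simulated trials.

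| Size of d | Rejection rate, no clobetasol-period change | Power, true change 1.0, d in the opposite direction |
|---|---|---|
| 0 | 0.010 | 93% |
| 0.25 | 0.020 | 83% |
| 0.50 | 0.052 | 65% |
| 0.75 | 0.11 | 42% |

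**6. Precision by arm.** With the formula of step 1, power at effect size 1.0 and 0.01 is 35% for 8 pairs, 50% for 10, 64% for 12 and 87% for all 17.

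**The case against.** **Pooling is implied, not prescribed.** The 20-pair example is a conditional power illustration, and a by-arm analysis is not ruled out. This stands as a limit on wording: the plan does not commit to a pooled test. But the example is the only tissue analysis described, it cannot come from one arm, and the arm safeguards given for OMRS are absent.

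**The analysis is secondary and labelled exploratory.** This is true and limits the severity. The label does not tell a reader that the pairs measure different intervals.

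**The clobetasol-first pairs are not a pure 28-day measure either.** A reader might take them as the clean estimate and discard the rest. The documents do not support that. Section 3.3.1 says "Pre-treatment tests should be performed within 1 month prior to enrollment on the trial unless otherwise stated", while Appendix G has a screening column of day -7 to 0, so untreated time can precede day 0 in both arms. Neither arm has a concurrent untreated tissue control over the clobetasol weeks. What differs by arm is the extra 14 days on placebo. Relying on the clobetasol-first pairs alone would also give up about half the data.

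**The size is not documented.** A reader might use the placebo response rate assumed for power, "about half that amount, 35%, on the placebo arm", as the size of the bias. It is an OMRS planning figure, not a tissue quantity. Nor can a weakening of a tissue–OMRS correlation be derived: the plan specifies no such correlation, and the variances needed are not given.

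**Conclusion.** The interval mismatch follows directly from the schedule: nominally 42 days against 28 for tissue, and 28 in both arms for OMRS response. As Section 10.2 stands, change during the placebo weeks can be attributed to clobetasol, and in placebo-first patients tissue change and response are not measured over the same period.

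The size is unknown. The share m/20 rests on additivity and on how the pairs divide between arms, and the simulated rates rest on assumed values of d. They show that a moderate placebo-period shift would matter in either direction; they do not show that one is expected.

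Stronger conclusions that a reader might draw do not hold. The primary OMRS endpoint and the blinded day-14 comparison are unaffected. The 93% power figure is not an error. Profiling of baseline tissue alone is not touched by the interval. Blood and saliva are collected at the unblinding visit, and nothing in the documents sets a wrong baseline for them. This is worth correcting before analysis, but it does not undermine the trial.

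**What to change.** Amend the biopsy paragraph of Section 10.2; no biopsy is added.

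- **By arm.** Report paired tissue change separately by randomized arm. Label placebo-first pairs as placebo plus clobetasol over about 42 days. Show an overall result only alongside the by-arm results, either with arm as a factor or under the p>0.30 similarity check already used for OMRS.
- **Matching intervals.** When tissue change is related to clinical response in placebo-first patients, show the OMRS change from day 0 to day 42 as well as the protocol's day-14-based response. The first matches the tissue interval; the second keeps the protocol's definition of response to clobetasol. Both use scores already collected.
- **State the precision.** By-arm estimates are weaker: about 50% power with 10 pairs at effect size 1.0 and 0.01, against 93% with 20. By-arm reporting discloses the placebo-period contribution but cannot isolate the clobetasol effect within the placebo-first pairs.

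The number of pairs is itself uncertain: Section 10.2 calls the biopsies required, Appendix G marks the second as optional, and Section 11.5.2 makes biopsy optional for pediatric patients. These passages should be reconciled. Otherwise the cost is SAP wording and analysis time.

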## **11 HUMAN SUBJECTS PROTECTIONS**

## 11.1 RATIONALE FOR SUBJECT SELECTION

No subjects will be excluded from participation based on sex, race or ethnicity. The study will be open to all subjects who satisfy the inclusion criteria and provide an informed consent to the protocol. From previous transplant protocol recruitment patterns at NIH we expect that over 80% of patients in this study will be adults over 18.

Recruitment: Subjects will be primarily recruited from NIH Clinical Center hematopoietic stem cell transplant clinics but could be referred from the outside institutions.

## **11.2 PARTICIPATION OF CHILDREN**

This study will be limited to subjects aged 12 or older. Given the preliminary nature of the study and requirement for precise compliance with the instructions to minimize swallowing and systemic absorption of clobetasol, children < 15 who are less likely to comply will be excluded. In addition, due to the risk of swallowing, oral rinses such as topical fluorides are not recommended for young children.

